Study Design	In this single centre study, assessment of three theoretical enhancements to visual acuity testing 1) crowding-enhanced letters, 2) crowded-enhanced contrast-modulated letters and 3) measurement of crowding distance, will be tested using clinical tests in a control group and in amblyopic children. Results from these 3 tests will be compared to each other and to those from the Sonksen logMAR Test (SLT) the current clinical standard, as measured by a clinician. Comparisons across test, and between participant groups, will enable us to determine the optimal test, or combination of tests, for detecting amblyopia. Visual acuities and crowding distance will be measured prospectively in a randomised controlled trial. Results will also be obtained in a control group, a sample of false-positive referrals to the hospital, and compared to that already obtained on normal healthy children (Waugh et al., 2018).					
	The testing will take place in a clinical room neighbouring the ACPOS (Addenbrooke's Community Paediatric Ophthalmology Service) clinic, which is hosted within the University Eye Clinic at Anglia Ruskin University (ARU).					
Study Participants	Test participants; 42 Male and female, 3 to 11-year-old children diagnosed as having amblyopia (21 strabismic and 21 anisometropic) by clinicians within Addenbrookes Community Paediatric Ophthalmology Service (ACPOS), hosted by the University Eye Clinic at Anglia Ruskin University (ARU) will be recruited.					
	Control Participants; 21 Male and female, 3 to 11-year-old children who have either been falsely referred into ACPOS (Addenbrookes Community Paediatric Ophthalmology Service) by the national vision screening service, but who are subsequently found to have satisfactory visual function; or visually healthy volunteers who have already passed vision screening will be recruited.					
	All participants must be able to perform the Sonksen logMAR Test (SLT) either verbally, or by using a matching card.					
Planned Size of Sample (if applicable)	Total participant pool: n =63 Anisometropic amblyopes n =21; Strabismic amblyopes n =21; Control group n =21.					

Follow up duration (if applicable)	This project requires one visit by each participant. However participants may choose to participate more than once (up to a maximum of 3 times) during the recruitment and testing period (within the 2 year data collection period).

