In the Sonksen logMAR Test (SLT), a single line of 4 letters separated from each other by 5 stroke-widths (or 1 optotype width), is contained within a box, separated from the letters also by 5 stroke-widths.

Recognition of target optotypes created by contrast-differences (second-order stimuli) is prone to greater crowding effects than is recognition of optotypes created by luminancedifferences (first-order stimuli) (Wong, Levi and McGraw, 2001, 2005; Chung, Li and Levi, 2008; Hairol, Formankiewicz and Waugh, 2013). This effect is present in normal vision, however even greater visual losses for contrast-defined targets, as well as stronger crowding effects, have been reported in amblyopia (Chung, Li and Levi, 2008). By presenting a contrastmodulated (CM) target letter (H, O, T or V) surrounded by four other letters (U, A, L, C) placed 1 stroke-width away (in the modified Cambridge Crowding Test arrangement), this research aims to examine whether this second-order vision test will exaggerate differences between the eyes of amblyopic children, when compared to those measured in visually 'normal' children. The results will again be compared to those obtained with the Sonksen logMAR test (SLT), a first-order vision test, to compare their sensitivities to amblyopia detection.

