"Is there a difference in sensitivities of these modifications to detecting strabismic amblyopia versus anisometropic amblyopia?"

Hypotheses

Null hypothesis 1 (H1₀): The new crowding tests do not offer better sensitivity to inter-ocular differences in acuity in amblyopic children, than the Sonksen logMAR test (SLT).

Alternative hypothesis 1 (H1_a): The new crowding tests do offer better sensitivity to interocular differences in acuity in amblyopic children, than the Sonksen logMAR test (SLT).

Null hypothesis 2 (H2₀): There is no difference in the sensitivities of the new tests to detecting strabismic amblyopia, versus anisometropic amblyopia.

Alternative hypothesis 2 (H2_a): There is a difference in the sensitivities of the new tests to detecting strabismic amblyopia, versus anisometropic amblyopia.

The following steps will be taken in order to complete this project:

- 1. Critically appraise relevant literature about the effects of crowding on visual acuity in normal and amblyopic adults and children for first-order and second-order optotypes.
- 2. Design a study to incorporate three suggested modifications to current visual acuity and crowding tests, in a sample of child control and amblyopic participants.
- 3. Statistically analyse the results, comparing those obtained on control and amblyopic children, as well as with data already gathered from normal healthy children. Data from the new tests will be compared with each other and with those obtained using the standard clinical vision test (the Sonksen logMAR Test: SLT).
- Accept or reject the given null hypotheses and discuss impact on clinical practice in a written thesis, as well as disseminate results at scientific conferences and in scientific peer-reviewed journals.

Study design, methods of data collection and data analysis

Study design

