Following completion of the vision tests, participants will be asked if they wish to be involved again with the study. If they do, then they will be tested again following their next Orthoptic review with the ACPOS clinic, or at a time that suits the family best. If they do not, this is the end of their participation.

Consideration of measurement tools, validity and reliability

The results will be generalizable to the entire UK screening population of 3 to 11-year-olds, due to the use of a control group, ensuring external validity.

Participant bias will be controlled and intra-observer reliability maximised using the rigorous set of forced-choice psychophysical testing procedures described above and a single specialized researcher. The researcher is a qualified clinical Orthoptist with many year's experience working with children in vision screening clinics, ensuring that the results will be obtained as accurately and consistently as possible. Test/re-test reliability is ensured by the use of randomization of the order in which the eyes are examined, and counterbalancing the order of the experiments.

Statistical consideration and Data management and analysis

Anonymised data from the 3 experiments will be stored digitally on the experimental computer, which is password protected and only accessible to members of the research team. Data will be compiled in an Excel spreadsheet, ready for analysis.

The data will be analysed using SPSS or Statistica with Repeated Measures Analysis of Variance models. Visual acuities, crowding and critical spacing estimates will be compared between normal and amblyopic groups. Confirmation of normality and sphericity will be assessed with a Shapiro-Wilk test and Mauchley's Test of Sphericity and where necessary, error rates will be adjusted with a Huynd-Feldt Correction in order to ensure that type 1 errors (incorrect rejection of the null hypothesis) are less likely. The rate of improvement of visual acuity, crowding and critical spacing over the treatment period will also be compared (in those participants who opt to complete more than one assessment session) between the three modified tests, and the SLT.

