The effect size is set at 0.100 logMAR, which is the minimum inter-ocular difference that should exist for the participant to be classified as amblyopic (Elliott and Firth, 2009). The standard deviation of the visual acuity measure is set as ± 0.100 logMAR. In adults, visual acuity repeatability measures of ± 0.1 logMAR have been found (Klein et al, 1983; Arditii & Cagenello, 1993; Siderov & Tiu, 1999). Lalor (2018), who used staircase procedures like those proposed, found for children aged 3 to 16 years, standard deviations of ± 0.06 logMAR. Pilot studies with the Crowding Distance Test have suggested even lower standard deviations of the test measures (Waugh et al., 2018).

Using a standardarised effect size of 1 (effect size/sd of measure; or Cohen's d of 1), a significance level or probability of committing a type 1 error (incorrect rejection of null hypothesis), of 0.05; and the probability of committing a type 2 error (incorrect acceptance of null hypothesis) of 0.2 (power of 0.8), a sample size of n=16 participants in each group

30

(amblyopes and control participants) will be required to achieve statistical significance, if a difference exists.

In brief, the data generated will be analysed using a Repeated Measures Analysis of Variance (with Huyndh-Feldt correction for violation of sphericity of variance). In this procedure means are compared. Also post-hoc Tukey comparisons between groups can be made; or a Dunnett test comparing each group (anisometropic; strabismic) to the control group (normal controls)

The above calculation is sufficient for a comparison of means. The second hypothesis involves three distinct groups with independence of observation. An alternative way to estimate sample size is to conduct a one-way ANOVA using an effect size *Cohen's f*, is set at 0.4 (for "large" effect size) to examine for large effect sizes. Once again, the significance level or probability of committing a type 1 error is set at 0.05, and the probability of committing a type 2 error is set at 0.2, to yield a study power of 80%.

Following this power calculation, a sample size of n=21 participants in each group (anisometropic amblyopes, strabismic amblyopes and control participants) will be required to achieve statistical significance, if a difference exists.

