These figures produce an estimated total sample size of n=32 for testing Hypothesis 1 (16 amblyopes and 16 controls), and n=63 for testing Hypothesis 2 (21 anisometropic amblyopes, 21 strabismic amblyopes and 21 controls).

In order to fulfil both these criteria for hypotheses 1 and 2, and achieve statistical significance, we will recruit n=21 in each group (anisometropic amblyopes, strabismic amblyopes and control participants), with a total recruitment number n=63.

Recruitment and identification of participants:

The study will be publicised in a number of ways.

- 1. A poster will be displayed in the waiting room of the ACPOS clinic in order to raise awareness of the study to those who attend the clinic (Appendix 1).
- 2. Clinicians / the direct care team at ACPOS, will identify eligible participants during their clinical appointments, and offer them a study information leaflet. ACPOS will be the Patient Identification Point (PIC). An application will be made for the Principal Investigator to have a research passport (letter of access/ honorary research contract) in order to help identify potentially suitable participants attending the ACPOS clinic. The Principal Investigator is suitable for this task as she worked as the clinician in this clinic prior to starting this study.

Interested persons will be given the parent / guardian and paediatric information sheets (Appendix 1) and their medical history checked to ensure they meet all the inclusion criteria and none of the exclusion criteria, prior to recruitment. For ACPOS individuals who do not wish to take part, the clinician will add an addendum to the participant's clinical notes to ensure that the participant is not approached again as a potential participant.

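### The 80% power quoted for Hypothesis 1 belongs to an amblyope-versus-control comparison; the gain of the new tests over the SLT was never sized

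*Combined protocol and SAP*

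**What the plan says.** The Hypotheses section gives the first null hypothesis as "The new crowding tests do not offer better sensitivity to inter-ocular differences in acuity in amblyopic children, than the Sonksen logMAR test (SLT"). This compares tests within amblyopic children.

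The Sample Size section sizes it with a t-test at two-sided 0.05 and 80% power. On the effect it says "The effect size is set at 0.100 logMAR, which is the minimum inter-ocular difference that should exist" for a child to be classed as amblyopic. On spread it says the "standard deviation of the visual acuity measure is set as ± 0.100 logMAR", and it adds that an earlier staircase study "found for children aged 3 to 16 years, standard deviations of ± 0.06 logMAR". The standardised effect is therefore 1, which leads to 16 in each of two groups, amblyopes and controls. The section then gives an "estimated total sample size of n=32 for testing Hypothesis 1 (16 amblyopes and 16 controls").

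The only other calculation is a three-group one-way ANOVA for Hypothesis 2 (Cohen's f of 0.4, 21 per group). It sets the recruitment target of 63: 42 amblyopes and 21 controls.

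Two other places bear on what Hypothesis 1 means. The synopsis, under Study Design, says: "Comparisons across test, and between participant groups, will enable us to determine the optimal test". The Rationale asks whether the contrast-modulated test will "exaggerate differences between the eyes of amblyopic children, when compared to those measured in visually" normal children. The statistical section says: "Visual acuities, crowding and critical spacing estimates will be compared between normal and amblyopic groups".

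**The concern.** The hypothesis compares tests, but the calculation attached to it compares groups. Each input shows the mismatch:

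- **Effect.** 0.100 logMAR is the IOD at which a child counts as amblyopic. A group difference of about that size follows from how the groups are formed and says nothing about improvement over the SLT.
- **SD.** 0.100 logMAR describes a single acuity measure. The Hypothesis 1 contrast, IOD on a new test minus IOD on the SLT, is built from four thresholds.
- **Missing inputs.** Neither document section gives a worthwhile gain over the SLT, or an SD or correlation for the between-test contrast.

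This is the main research question. As written, a reader is told it has 80% power. If no advantage over the SLT is found, there is no stated detectable gain against which to judge whether a useful gain was ruled out or merely missed.

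**Working it through.** **1. Reproduce the plan's figure.** Two independent groups, d = 0.100/0.100 = 1, two-sided 0.05, 80% power, normal approximation: n per group = 2 × (1.960 + 0.842)² / 1² = 15.7, rounded up to 16. By the exact t-test, power is 78.1% at 16 per group and 80.7% at 17. A paired test at d = 1 would need only 10 children. So 16+16 is a between-group figure, and its arithmetic holds.

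**2. Inputs for the Hypothesis 1 contrast.** The documents give none, so these are assumptions. If the four thresholds (two eyes, two tests) are independent, each with SD s, the contrast SD is √4 × s = 2s. With the two SDs in the Sample Size section, s = 0.06 gives 0.12 and s = 0.10 gives 0.20. Gains of 0.05 and 0.10 log units are illustrations.

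**3. Two readings of the contrast.** The Hypotheses wording points to a paired contrast in the 42 amblyopes. The synopsis and Rationale also allow that contrast to be compared with controls (group-by-test, 42 v 21, equal SD in both groups assumed).

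**4. Detectable difference at 80% power, two-sided, noncentral t.** Noncentrality is d√42 on 41 df (paired) and d/√(1/42 + 1/21) on 61 df (group-by-test). Log-unit values are for contrast SD 0.12 / 0.20.

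| Alpha | Paired, n=42 | Log units | 42 v 21 | Log units |
|---|---|---|---|---|
| 0.05 | 0.44 SD | 0.053 / 0.089 | 0.76 SD | 0.091 / 0.152 |
| 0.05/3 | 0.52 SD | 0.062 / 0.103 | 0.89 SD | 0.106 / 0.177 |
| 0.05/4 | 0.54 SD | 0.064 / 0.107 | 0.92 SD | 0.110 / 0.183 |

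The 0.05/3 row applies if three new tests are each compared with the SLT. The 0.05/4 row applies if the trigram and repeated arrangements of the Crowding Distance Test are both tested.

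**5. Power at two-sided 0.05, for contrast SD 0.12 / 0.20.**

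| Assumed gain | Paired, n=42 | 42 v 21 | Paired, n=16 | 16 v 16 |
|---|---|---|---|---|
| 0.10 | >99% / 89% | 87% / 45% | 88% / 46% | 63% / 28% |
| 0.05 | 75% / 35% | 34% / 15% | not needed here | not needed here |

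Even if 0.10 were taken as the gain over the SLT, the quoted 16+16 would not yield a fixed 80% under either reading. At the planned size, a gain of 0.10 keeps 80% power up to a contrast SD of 0.10/0.443 = 0.226 (paired) or 0.10/0.761 = 0.131 (group-by-test).

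**6. Precision (95% CI half-width).** Paired: 2.020 × SD/√42 = 0.037 / 0.062. Group-by-test: 2.000 × SD × √(1/42 + 1/21) = 0.064 / 0.107.

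**7. If 16+16 was meant for IOD.** With independent eyes at SD 0.10, the IOD has SD 0.10 × √2 = 0.141, so d = 0.71. Exact t power is then 49% at 16 per group and 74% at 42 v 21.

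**The case against.** The strongest reply is that little depends on this. Hypothesis 2 sets the total of 63, and on the assumptions above the most direct reading of Hypothesis 1 has 89% to over 99% power for a gain of 0.10. A null result would in any case be read from its confidence interval. That is fair, and it is why no claim of underpowering is made. It does not rescue the 80% statement, because the protocol says 63 was chosen to satisfy the criteria for both hypotheses, and the Hypothesis 1 criterion answers a different question.

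A second reply is that the 45% for group-by-test is a harsh case: it takes the less direct reading, the larger SD, and equal SDs in both groups. If controls had 0.12 and amblyopes 0.20, Welch power would be about 68%. This stands as a caution; 45% is one end of a range.

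A third concerns the SDs. The protocol does not say whether 0.06 is within or between children, and it reports still lower values for the Crowding Distance Test. Positive correlation across eyes and tests would lower the contrast SD. True variation in gain between children would raise it: adding a between-child SD of 0.15, itself an assumption, moves the paired detectable gain to about 0.085 or 0.111. The SLT value for clinic patients is also the most recent clinic result rather than a same-session one. So the standardised 0.44 is firm and the log-unit figures are indicative.

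Finally, the planned repeated-measures ANOVA and Bland-Altman analysis do involve comparisons between tests. Analysing a contrast does not size it.

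**Conclusion.** The concern holds, and the text should be corrected. The 16+16 calculation sizes an amblyope-versus-control difference. It sizes neither the paired contrast with the SLT nor that contrast compared between groups, and nothing else in the protocol does. This rests on the protocol's own wording and on reproducing its figure, so confidence is high.

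How much power Hypothesis 1 really has cannot be settled from the documents. Over the assumed gains (0.05 to 0.10) and contrast SDs (0.12 to 0.20), power at the planned size at two-sided 0.05 runs from 15% to over 99%. Where it falls depends on choices and inputs the protocol does not state.

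**What to change.** 1. Relabel 16+16 as the amblyope-versus-control comparison of acuity, say which eye is compared, justify 0.100 as a difference in acuity, and stop citing the figure as power for Hypothesis 1. If IOD is meant, give an IOD SD and the between-eye correlation behind it.
2. Define the Hypothesis 1 contrast as IOD on the new test minus IOD on the SLT, on a log10 scale, tested as a paired contrast in the 42 amblyopes. State whether comparing it with controls is also part of Hypothesis 1, and which Crowding Distance Test arrangement (trigram or repeated) forms its IOD.
3. Replace the 80% claim with wording such as:

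> *Forty-two amblyopes give 80% power for a standardised paired difference of 0.44 (0.52 at 0.05/3 if three new tests are each compared with the SLT), about 0.05 or 0.09 log units if the contrast SD is 0.12 or 0.20. The group-by-test contrast at 42 v 21 needs 0.76, about 0.09 or 0.15, assuming equal SD in both groups. These SDs are assumptions (four independent thresholds of SD 0.06 or 0.10). No SD for this contrast in amblyopic children is available, and it may be larger.*

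   If both arrangements are tested, use 0.05/4 (0.54 paired, 0.92 group-by-test).
4. Report the contrast with its 95% confidence interval.

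The cost is one rewritten paragraph and two decisions by the authors: whether controls enter Hypothesis 1, and which arrangement is used. No extra children or visits are needed and the total of 63 is unchanged. The authors lose a fixed 80% claim and gain detectable differences that openly rest on assumed SDs. Those differences are larger if group-by-test is chosen.

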Planned Study Period	It is planned that recruitment and testing will take place over 2 year period. (See Gantt Chart for estimated project delivery dates).
Research Question/Aim(s)	This study aims to investigate whether proposed modifications to visual acuity tests will offer better sensitivity to the detection of amblyopia than the Sonksen logMAR test (SLT). It will also determine whether differences in outcomes occur for anisometropic, versus strabismic amblyopes.

FUNDING AND SUPPORT IN KIND

FUNDER(S) (Names and contact details of ALL organisations providing funding and/or support in kind for this study)	FINANCIAL AND NON FINANCIALSUPPORT GIVEN				
 Anglia Ruskin University (via The Doctoral School) [name] Director of Doctoral School Research and Innovation Development Office Anglia Ruskin University, Chelmsford [name] [contact] 	The Research Supervisor/Chief investigator ([name] [name]) has been awarded a Vice Chancellor's Studentship to provide fees and a living stipend to support a PhD student, ([name]), throughout the course of this study.				
[contact] 2) Anglia Ruskin University via Quality Related Research Funds from HEFCE (Higher Education Funding Council for England) to FST and Anglia Vision Research.	Quality Related Research Funding from HEFCE awarded to ARU has been approved for the Research Supervisor to reimburse participants' parents/carers for their time (£10 per participation visit in the form of an amazon voucher) for this project.				
[name] Deputy Dean (Research and External Income) Faculty of Science and Technology Anglia Ruskin University [name] [contact]	Quality Related Research Funding has been approved for the Research Supervisor to cover the cost of computer hardware and software required for the execution and analysis of data generated from this project.				

Contact on behalf of the Sponsor

[name], Chair of Faculty of Science and Technology Research Ethics Panel (FST FREP), Department of Psychology, Faculty of Science and Technology, Anglia Ruskin University, Cambridge [name] [contact]

ROLE OF STUDY SPONSOR AND FUNDER

The Sponsor and the Funder for this project is Anglia Ruskin University (ARU).

The Principle Investigator on this study is a PhD student ([name]) funded through an ARU Vice-Chancellor's PhD Studentship, awarded to the Chief investigator / Research Supervisor ([name] [name]). The award funds the PhD student's fees and bursary.

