Crowding is clearly demonstrated in peripheral vision in normal healthy individuals; middle letters of a word are harder to distinguish than letters on either end. However its presence has been confirmed in central vision of individuals with strabismic amblyopia, and to a lesser extent, those with anisometropic amblyopia (Stuart and Burian, 1962; Flom, Weymouth and Kahneman, 1963; Levi and Klein, 1985; Hess, Dakin and Kapoor, 2000; Kemper and Patel, 2011; Spiegel et al., 2013; Lev, Yehezkel and Polat, 2014) (Flom, Weymouth and Kahneman, 1963; Levi and Klein, 1985; Spiegel et al., 2013; Hess, Dakin and Kapoor, 2000; Kemper and Patel, 2011; Stuart and Burian, 1962; Lev, Yehezkel and Polat, 2014). This means that crowding can be incorporated into vision charts in a clinical setting, as its presence will enhance visual acuity loss in the central vision of amblyopic eyes, but not in normal eyes. Traditionally, high contrast visual acuity charts have been used to examine visual acuity limits. In amblyopia however, central vision can be much more restricted by crowding from visual clutter, than by visual acuity itself (Song, Levi and Pelli, 2014). Although currently available clinical vision charts attempt to incorporate crowding features, they are not successful at doing so in normal adults and some anomalous patients, and it is thought that they could be substantially improved (Hairol, Formankiewicz and Waugh, 2013; Formankiewicz and Waugh, 2013; Song, Levi and Pelli, 2014; Pelli et al., 2016). The proposed study will test whether

3

recent suggestions for theoretical improvements in vision tests will actually result in more favourable outcomes with respect to diagnosing amblyopia, in the target developing population, i.e., young children.

Rationale

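### The 80% power claimed for Hypothesis 2 belongs to a three-group test that includes controls, not to the strabismic-versus-anisometropic comparison that the hypothesis states.

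*Combined protocol and SAP*

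**What the plan says.** The study summary sets the secondary aim: "It will also determine whether differences in outcomes occur for anisometropic, versus strabismic amblyopes". The Hypotheses section gives the matching null: "There is no difference in the sensitivities of the new tests to detecting strabismic amblyopia, versus anisometropic amblyopia". Neither statement mentions controls.

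The Sample Size section treats the same hypothesis as a three-group problem: "The second hypothesis involves three distinct groups with independence of observation". It continues "An alternative way to estimate sample size is to conduct a one-way ANOVA", with Cohen's f = 0.4, a type 1 error of 0.05 and power of 80%. The result is 21 per group, summarised as "n=63 for testing Hypothesis 2 (21 anisometropic amblyopes, 21 strabismic amblyopes and 21 controls".

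For comparisons between groups, that section says "Also post-hoc Tukey comparisons between groups can be made", and then offers an alternative: "or a Dunnett test comparing each group (anisometropic; strabismic) to the control group (normal controls". The data analysis section plans repeated-measures ANOVA and speaks of comparing normal and amblyopic groups. It names no contrast for Hypothesis 2.

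**The concern.** A one-way ANOVA over three groups rejects when any of the three means differs. With controls as one group, it can reject purely because amblyopic children differ from controls. Its power says nothing definite about the difference between the two subtypes, which is what Hypothesis 2 asks.

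The protocol commits the team to accepting or rejecting each null hypothesis. A non-significant subtype comparison could then be reported as the outcome of an 80%-powered test, and read as evidence that the new tests work equally well in both subtypes, when its real power is unstated.

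The follow-up text adds to this. Tukey includes the strabismic-anisometropic pair; Dunnett against control does not. One of the two permitted options would leave Hypothesis 2 untested.

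**Working it through.** **Inputs from the Sample Size section:** three groups of 21, f = 0.4, two-sided alpha 0.05, target power 0.80. All means below are in units of a common SD.

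**1. Reproduce the plan's figure.** Noncentral F with λ = f²N = 0.16 × 63 = 10.08 on 2 and 60 df gives power 0.798. With 22 per group it is 0.818. So 21 per group is right, to rounding, for the test named.

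**2. What f = 0.4 implies for the subtypes.** Let g be the gap between the subtype means and c the distance of the control mean from their midpoint. Then

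f² = g²/6 + 2c²/9 = 0.16.

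- Identical subtypes: g = 0, so c = √0.72 = 0.849. Omnibus power is still 0.798 although the Hypothesis 2 null is true.
- Largest possible gap: c = 0 (controls midway), so g = 0.4√6 = 0.980.
- Anisometropic mean equal to controls: c = g/2, so 2g²/9 = 0.16 and g = 0.849.
- Equal spacing, controls at one end: c = 3g/2, so 2g²/3 = 0.16 and g = 0.490.

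**3. Power of the subtype contrast, 21 against 21.** The noncentrality is g√(21/2) = 3.240g. The unadjusted test uses t on 40 df (critical value 2.021). Tukey uses the three-group error term on 60 df (critical t 2.403).

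| Pattern (all with f = 0.4) | g | Unadjusted | Tukey |
|---|---|---|---|
| Subtypes identical | 0 | 5% | 1.9% |
| Equal spacing, controls at one end | 0.490 | 34% | 22% |
| Anisometropic = controls | 0.849 | 77% | 64% |
| Controls midway | 0.980 | 87% | 78% |

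The first row is a false-positive rate, not power. It is listed because the omnibus test claims 80% there.

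No pattern with f = 0.4 gives the Tukey pair 80%. Unadjusted power reaches 80% at g = 0.886, which requires c ≤ √[(0.16 − 0.886²/6) × 9/2] ≈ 0.36 SD. If both subtypes lie on the same side of controls, then c ≥ g/2 and g cannot exceed 0.849, so power is at most 77% (64% with Tukey).

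**4. Power by assumed standardised difference d, 21 against 21.**

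| d | Unadjusted | Tukey | Bonferroni over three new tests |
|---|---|---|---|
| 0.8 | 72% | 58% | 54% |
| 1.0 | 89% | 80% | 77% |
| d giving 80% power | 0.886 | 1.004 | 1.036 |

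**5. On the logMAR scale.** The SD of an inter-ocular difference is not given, so d = 0.886 can be converted only conditionally:

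- SD 0.06 (the children's acuity SD cited in the plan): 0.886 × 0.06 = 0.053.
- SD 0.10 (the plan's working value): 0.089.
- SD 0.10 × √2 = 0.141 (a difference of two independent eyes): 0.125.

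**The case against.** The best defence has four parts.

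- **Tukey is in the plan and contains the right pair, and the one-way ANOVA is offered only as a way to size the study.** Both are true. But Tukey is only one of two options, and the sizing calculation is the sole source of the 80% attached to Hypothesis 2.
- **Detecting a subtype implies a reference to controls, so three groups are natural.** Controls do have a role in showing detection. Hypothesis 2 as worded still sets one subtype against the other, and the omnibus F does not isolate that contrast.
- **The comparison may be adequately powered.** This stands. At d = 1, the effect used for Hypothesis 1, 21 against 21 gives 89% unadjusted and 80% with Tukey. The plan does not assume that effect for the subtype difference. Its Background reports foveal crowding in strabismic amblyopia "and to a lesser extent, those with anisometropic amblyopia". That suggests controls lie towards one end rather than midway, though it gives only a direction, and for crowding rather than for these test outcomes.
- **The logMAR conversions borrow SDs of acuity measures.** This is fair. They show how much depends on an unstated SD and should not enter the protocol as detectable differences without a justified SD.

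None of these points supplies a power for the Hypothesis 2 comparison.

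**Conclusion.** The concern holds. The plan's 80% is a correct figure for a three-group omnibus test and is not the power of the strabismic-versus-anisometropic comparison. This does not show that Hypothesis 2 is underpowered; it shows that its power is unknown. Under the plan's own f = 0.4 it can be as high as 87% unadjusted (78% with Tukey) and falls to 34% (22%) with equally spaced means.

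The figures assume normal data with equal SDs, 21 complete children per subtype and a single between-group contrast; they do not model the planned repeated-measures analysis. Every subtype difference used is an assumption. The point affects the secondary question only and should be corrected before analysis.

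**What to change.** 1. State that Hypothesis 2 will be tested by the strabismic-versus-anisometropic contrast on the inter-ocular difference. Say which of the new tests it covers and how multiplicity is handled.
2. State that neither the omnibus F nor Dunnett against control is the test of Hypothesis 2.
3. Replace the 80% statement for Hypothesis 2 with what 21 per subtype delivers: 80% power for d of about 0.89 for one unadjusted contrast, 1.00 with Tukey, or 1.04 with Bonferroni over three tests. Keep the ANOVA calculation only if it is labelled as the power to detect any difference among three groups.
4. If the sponsor prefers a subtype-by-test interaction (new test minus Sonksen), give its power over a range of the between-test correlation r, which the documents do not state. With equal SDs the 80% detectable difference is 0.886√[2(1 − r)]: 1.25 at r = 0, 0.89 at r = 0.5 and 0.56 at r = 0.8, in SDs of one inter-ocular difference.

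The cost is wording. The total stays at 63 and no more children are tested. The sponsor must accept a less favourable power statement for Hypothesis 2 and commit in advance to one contrast and one multiplicity rule.
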